## **5.8 Early Termination**

Subjects can be discontinued from the study for the following reasons:

- Failure to comply with the protocol requirements
- Pregnancy (followed on study but off study drugs see Section 10.5)
- Development of a serious adverse event (SAE) related to research
- Development of a Grade 3 or greater allergic reaction to rifaximin or develops signs and symptoms of an immediate hypersensitivity reaction to rifaximin
- Development of any medical or psychosocial condition that the study investigators deem would be detrimental for the subject to continue on the study
- Withdrawal of informed consent

If subjects are discontinued from the study during the treatment phases they will be replaced according to the prior randomization.

## **5.9 Pregnancy and Follow-up Visit**

If the subject becomes pregnant while on the study, the subject will be taken immediately off study product, the blind will be broken, and the subject will be followed on-study for safety until delivery. She will be asked to return every 4 weeks for safety laboratory monitoring (including ALT, complete blood count with differential, platelet count, BUN, and creatinine) and a targeted history will be obtained and directed physical performed as warranted.

**TABLE 1: Schedule of Events**

Procedures	SCREENING			STUDY PHASE 1						STUDY PHASE 2					
	Screen # 1	Screen # 2	Gut Bio psy	Day 0	Day 3 (optional)	Day 7	Day 14	Day 28	Wash-out	Day 0	Day 3 (optional)	Day 7	Day 14	Day 28	Final visit
Window			-30 day			+/- 3 days	+/- 3 days	+/- 3 days	+2 weeks			+/- 3 days	+/- 3 days	+/- 3 days	2 wks
Informed Consent	X														
Complete history and physical*		X													
HIV testing if needed	X														
Safety Labs **															
PT/INR		X					X						X		
CBC w/differential, platelet count		X		X	X	X	X	X		X	X	X	X	X	X
BUN, Cr, electrolytes, LFTs		X		X				X		X				X	X
Urine pregnancy test if applicable/Urine analysis%		X		X	X	X	X	X		X	X	X	X	X	X
Hepatitis profile@		X													
Research related labs															
Immunophenotyping		X		X	X	X	X	X		X	X	X	X	X	X
HIV- 1- RNA level	X	X		X	X	X	X	X		X	X	X	X	X	X
Single copy assay	X	X		X	X	X	X	X		X	X	X	X	X	X
Soluble biomarkers of inflammation***		X		X	X	X	X	X		X	X	X	X	X	X
Markers of bacterial translocation#		X		X		X	X	X		X		X	X	X	X
Colonoscopy and gut biopsy\$			X					X						X	
General Processes															
Adherence counseling; pill counts		X		X	X	X	X	X		X	X	X	X	X	
Assessment of symptoms, targeted	X	X		X	X	X	X	X		X	X	X	X	X	X

history and physical ^															
Cross-over (treatment arms)									X						
Study product dispensing				X						X					
Sample Storage															
Sample storage		X		X		X	X	X		X		X	X	X	X
Stored Stool for fecal microbiome				X	X	X	X	X		X	X	X	X	X	X

Footnotes

- \*Comprehensive history and physical examination will be performed at screening visit 2
- \*\* Abnormal safety labs will be confirmed before subjects are excluded
- \*\*\* highly sensitive C reactive protein (hsCRP), D-dimer, interleukin-6 (IL-6), tumor necrosis factor alpha (TNF- $\alpha$ )
- ^interim assessments; physical exam as warranted
- # Plasma LPS, bacterial 16S rDNA, sCD14
- \$ Colonoscopy is optional and will be performed at baseline and upon completion of the rifaximin treatment and placebo treatment phases. The baseline colonoscopy can be performed in the 30 days prior to day 0. While those being performed at the end of the treatment phases, must be completed while the subject is on study drug/placebo and can be completed in the 3 days prior to the completion of drug/placebo.
- % If clinically indicated
- @ Testing for Hepatitis B and Hepatitis A antibody status will only be performed in those with prior unknown or non-reactive status. Results of hepatitis C RNA testing in the 8 weeks prior to screening visit 2 are acceptable and will not be repeated.

## 6 STUDY EVALUATIONS

### 6.1 Clinical Evaluations

A medical history will be obtained and physical examination will be conducted at the screening visit. At each visit symptoms will be assessed and physical exams performed if needed.

### 6.2 Laboratory Evaluations

Local evaluations will include complete blood count with differential, platelet count, coagulation profile, and a metabolic profile that includes liver and kidney function tests and electrolytes. Table 1 provides details of the time points at which these evaluations will be completed.

Study-related research testing will be performed primarily at the NIH or at their contract facility [Leidos Biomedical Research, Inc.]; fecal microbiome will be performed at the Uniformed Services University (USU). Study-related tests include:

- HIV-1- RNA levels by standard assay
- HIV-1- RNA level by single copy assay
- Immunophenotyping to include markers of immune activation. Immune activation will be assessed using the following parameters: co-expression of HLA-DR and CD38 on CD4 and CD8T cells, mono-expression of HLA-DR and CD38 on CD4+ and CD8+ T cells. Additional markers that may reflect cellular activation including Ki-67 expression on CD4+ CD8+ T cells will be investigated
- Soluble biomarkers of inflammation to include hsCRP, D-dimer, IL-6, and TNF- $\alpha$
- Microbial translocation products will be measured using LPS levels, sCD14, and bacterial 16S rDNA or bacterial RNA.
- Stool samples for evaluation of the fecal microbiome. All stool samples for the fecal microbiome will be done prior to the bowel preps. Total bacterial load, as well as relative numbers of specific organism (such as *B. fragilis*) will be examined.
- An optional colonoscopy will be performed to sample the gut mucosal tissue. Samples will be obtained from the left colon (rectosigmoid) and terminal ileum. A maximum of 60 tissue samples will be obtained from both the rectosigmoid and terminal ileum. All procedures will be performed by trained gastroenterologists. Samples will be obtained in pre-filled tubes by the gastroenterologist. All samples will then be shipped by study personnel to a central processing laboratory housed at the Frederick National Laboratory for Cancer Research, [name]. Gut mucosal biopsies will be processed as per standard procedures at the central laboratory and not at the sites. Gut mucosal biopsies will be examined for routine hematoxylin and eosin staining (H&E), immunohistochemistry,

quantitative HIV-DNA and RNA levels, phenotyping and genotyping of HIV-1-RNA, and quantitative enumeration of T cell populations to include numbers and proportion of CD4+ and CD8+ T cells, T cell activation markers (to include CD38 and HLA DR expression on CD4 and CD8 + T cells, Ki-67 expression). Mucosal biopsies will also be analyzed for NK cell populations.

Table 1 details the time points at which these evaluations will be completed.

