#### ***A potential role for rifaximin, a non-absorbable antibiotic***

The presence of bacterial products in blood is likely related to the extent of damage to the gut barrier[58]; it is not known whether the level or type of bacteria in the GI tract may also affect the level of translocation. Investigation of other inflammatory bowel diseases, such as ulcerative colitis or Crohn's disease, and hepatic encephalopathy offer some insights. For example, in a large longitudinal study, serum LPS-binding protein levels and sCD14 correlated with Crohn's disease activity, with increases occurring in individuals experiencing disease flares, and decreases occurring as disease activity was controlled[66]. Similarly, in subjects diagnosed with hepatic encephalopathy there is increased translocation of gut-derived endotoxin. The use of antibiotics, including rifaximin, has been associated with statistically significant increases in induction of disease remission in both these states [67].

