### **Research Labs and Procedures**

- Immunophenotyping to include CD4 count and cellular markers of activation (including CD4 count, HLA DR, CD38, co-expression of HLA DR and CD38 on CD4+ and CD8+ cells)
- Single copy assay & HIV-1 RNA levels
- Markers of bacterial translocation (LPS, bacterial 16S rDNA/bacterial RNA, sCD14)
- Soluble markers of inflammation (IL6, hsCRP, TNF $\alpha$ , D-dimer)
- Colonoscopy with gut biopsies is optional

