### **Research Labs and Procedures**

- Immunophenotyping to include a CD4 count and cellular markers of activation (including HLA DR, CD38, co-expression of HLA DR and CD38 on CD4 and CD8 cells)
- Single copy assay & HIV-1 RNA levels
- Soluble markers of inflammation (IL6, hsCRP, TNF $\alpha$ , D-dimer)

- Markers of bacterial translocation (LPS, bacterial 16S rDNA/bacterial RNA, sCD14)
- Colonoscopy with gut biopsy is optional

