## **5.7 Study-Related and Non-Study Related Procedures and Vaccinations**

Routine vaccinations (i.e. influenza) may be administered during the screening process or washout phase. Subjects receiving routine vaccinations during the washout phase will have their washout extended to 6 weeks. At each of these visits subjects will undergo interim evaluation of symptoms by study personnel and a targeted physical examination as deemed medically appropriate. Samples for the study are shipped from the University of Pittsburgh, NIH and Walter Reed sites to NCI for analysis. In the event of unforeseen logistical circumstances (e.g., because of a flight delay in sample shipment) resulting in a loss of samples necessary for analysis of the primary endpoint, and if the participants have already started phase 1 or 2 drug/placebo in

the interim, the participants will be asked to stop taking drug/placebo. They will undergo a four week washout and restart the respective study phase.

Gut mucosal biopsies via colonoscopy are optional and, if done, will be performed at baseline and upon completion of the rifaximin dosing and the placebo dosing phases (Days 28 of phases 1 and phase 2). If a subjects opts in for two of the three colonoscopies, these will be performed on approximately day 28 of phases 1 and 2, if a subjects opts for a single colonoscopy it will be performed on approximately day 28 of phase 2 of the study to maintain uniformity. As the relative representation of mucosal immunophenotypes and HIV-1-RNA levels can vary according to the location of the sampling site [61], multiple biopsies will be obtained during colonoscopy from the distal ileum and rectosigmoid (a total of 60 biopsies). For subjects enrolled at the NIH gut biopsies will be conducted under protocol 95-I-0027 entitled "Virologic and Immunologic Evaluation of Lymph Node, Tonsillar and Intestinal Biopsies, and Bronchoalveolar Lavage Fluid," as this protocol was designed to serve as a mechanism to obtain tissue samples.

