All subjects in whom a colonoscopy is to be performed will be instructed to abstain from receptive anal intercourse for 3 days prior to rectal biopsy, and for 7 days post-biopsy to minimize risk of bleeding complications. Participants also should abstain from administration of rectal medications (including over-the-counter medications) for 3 days prior to rectal biopsies. All visits during the dosing phases will be completed on the indicated days of the protocol within a 3 day window. The washout phase may be extended from 4 to 6 weeks if necessary (i.e., immunizations, transportation, etc.). The final study visit may be completed +/- 2 weeks of anticipated study completion.

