## **12 STATISTICAL CONSIDERATIONS**

### **12.1 Study Hypotheses**

This is a double-blind, randomized, crossover, placebo-controlled trial of rifaximin use in HIV-infected subjects. In this trial, ART-treated subjects with an undetectable viral load will be enrolled. The primary objective of this study is to compare the changes in sCD14 levels during the rifaximin phase of the study and compare it with the changes in sCD14 during the placebo phase of the study. Specifically the difference in sCD14 levels measured on Days 28 of treatment phase 1 and 2 will be used to assess rifaximin effect. Moreover to deal with a possible secular trend, the difference of differences (the difference of sCD14 levels measured on treatment phase 1 Days 0 and 28 and the difference measured on treatment phase 2 Days 0 and 28) will be examined as well.

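### Does the Day 28 sCD14 blood need to be drawn before bowel preparation, as the stool sample is?

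*Combined protocol and SAP*

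**What the plan says.** Section 6.2 fixes the order for the microbiome specimen: "All stool samples for the fecal microbiome will be done prior to the bowel preps". Nothing comparable is written for blood.

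The Day 28 lists in sections 5.4 (phase 1) and 5.6 (phase 2) contain the research blood, including sCD14, and then the procedure: "Colonoscopy with gut biopsies is optional" in phase 1 and "Colonoscopy with gut biopsy is optional" in phase 2. Neither list gives a sequence within the visit.

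Table 1, footnote $, says that the end-of-phase colonoscopy "must be completed while the subject is on study drug/placebo and can be completed in the 3 days prior to the completion of drug/placebo". Section 5.7 adds: "All visits during the dosing phases will be completed on the indicated days of the protocol within a 3 day window". Section 5.7 also places two colonoscopies at about Day 28 of each phase, and "if a subjects opts for a single colonoscopy it will be performed on approximately day 28 of phase 2".

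The primary contrast is in section 12.1: "Specifically the difference in sCD14 levels measured on Days 28 of treatment phase 1 and 2 will be used to assess rifaximin effect".

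**The concern.** The protocol protects an exploratory specimen from bowel preparation and leaves the primary-endpoint specimen unprotected. Read literally, the Day 28 blood may be taken after preparation and after as many as 60 biopsies. The Background gives a reason to wonder whether that matters: "The presence of bacterial products in blood is likely related to the extent of damage to the gut barrier". sCD14 is used here as a marker of the response to such products.

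A subject with a colonoscopy at both Day 28 visits would carry any constant shift in both samples, and it would cancel. A subject with one colonoscopy would carry it in phase 2 only. The planned difference of differences (section 12.1) uses the same Day 28 samples, so it would not remove the shift. At stake would be the precision of the primary comparison, and its validity if uptake differed between the sequences.

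**Working it through.** **Inputs from the documents.** SD 0.45, correlation 0.71, target difference 0.20 (all ×10⁶ pg/mL except the correlation), 40 evaluable subjects and type I error 0.05, from section 12.2. Two-sided testing, a one-sample Wilcoxon test on the Day 28 differences and equal allocation to the two sequences, from section 12.3.

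**Inputs that must be assumed.** The shift s in sCD14 when blood follows preparation or biopsy, and the fraction f of subjects shifted in phase 2 only. The documents give neither. The fraction is a product: share opting in × share with one colonoscopy × share bled after preparation. Two illustrations are 50% × 50% × 50% = 12.5% and 75% × 50% × 100% = 37.5%.

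**Step 1: reproduce the plan's power.** The SD of the paired difference is 0.45 × √(2 × (1 − 0.71)) = 0.343, so its variance is 0.1174. The two-sided paired-t power with n = 40 and difference 0.20 is 94.9%, which matches the stated 95%. The signed-rank test, simulated on the same inputs, gives 94.0%.

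**Step 2: what a phase-2-only shift does.** It enters the rifaximin-minus-placebo difference as +s for subjects who take rifaximin second and −s for those who take placebo second. With f equal in the two sequences:

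- mean contribution = ½ × f × s − ½ × f × s = 0
- added variance = f × s²

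**Step 3: paired-t power, n = 40.** SD = √(0.1174 + f × s²).

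| f | s | f × s² | SD of difference | Power |
|---|---|---|---|---|
| 0 | – | 0 | 0.343 | 94.9% |
| 12.5% | 0.1 | 0.00125 | 0.345 | 94.7% |
| 37.5% | 0.1 | 0.00375 | 0.348 | 94.3% |
| 25% | 0.2 | 0.0100 | 0.357 | 93.2% |
| 50% | 0.2 | 0.0200 | 0.371 | 91.4% |

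The last two rows use a shift equal to the entire target effect.

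**Step 4: the planned test.** The signed-rank test was simulated with 20 subjects per sequence and 200,000 runs per case, with shifted subjects split evenly between sequences. Power is 93.9% for s = 0.1 in 25% of subjects, and 92.9% and 91.7% for s = 0.2 in 25% and 50%. If shifted subjects arise at random instead of evenly, the lowest figure among these cases is 90.9% (s = 0.2 in 50%). Type I error is at or below 5.0% in all of them.

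**Step 5: chance imbalance between sequences.** With 20 subjects per sequence, the SD of the resulting bias is s × √(2 × 20 × f × (1 − f)) / 40. At f = 25% and s = 0.2 this is 0.2 × √7.5 / 40 = 0.014, against a target of 0.20.

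**Step 6: a yardstick.** If the assumed correlation were 0.68 rather than 0.71, the SD of the difference would be 0.45 × √0.64 = 0.360 and the power 92.9%. A change of 0.03 in one planning input costs 2.0 points, more than the 0.2 and 0.6 points lost in the s = 0.1 rows above.

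**The case for a change.** The best argument for acting is that acting is cheap and fits the protocol's own habits. The protocol centralizes assays to limit variability, bars immunomodulators because they might affect the primary outcome, and fixes the timing of a single colonoscopy for uniformity. One sentence on draw order would follow the same logic. It would also cover LPS, IL-6, TNF-α, D-dimer and hsCRP, which come from the same draw. Same-day order may be hard to recover afterwards.

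The silence in the text stands, and so does the possibility that single-colonoscopy subjects differ between phases. The rest is weaker:

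- **The causal step is missing.** The Background sentence concerns gut-barrier damage. It mentions neither preparation nor biopsy, and it goes on to say that an effect of bacterial level or type on translocation is not known.
- **The stool rule has its own reason.** Preparation acts directly on the stool specimen. A rule for stool does not imply that blood needs one, so the two are not inconsistent.
- **The affected group is limited.** Section 5.7 first describes a baseline procedure and one at the end of each phase, with two or one as alternatives. Anticoagulant users and subjects unfit for sedation cannot have the procedure. NIH biopsies run under a separate protocol that is not among the documents and may set an order.
- **A draw-order rule is not free of the same defect.** Drawing before preparation could move the blood up to 3 days earlier, and for single-colonoscopy subjects that would again happen in phase 2 only. It could also add a trip.
- **A check by exclusion would cost more than it protects.** Removing 12.5% or 37.5% of 40 subjects leaves 35 or 25, with paired-t power of 91.8% or 79.9%.

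**Conclusion.** No change is needed. The protocol leaves one operational detail open: the order of the Day 28 blood and bowel preparation. Site staff would ordinarily settle this when booking the visit, and the plan followed as written still gives a sound primary comparison.

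If preparation or biopsy shifts sCD14 at all, the consequence is added spread. Expected bias is zero and type I error is not inflated. The power loss is 0.2 to 0.6 points for an assumed shift of 0.1 in 12.5% to 37.5% of subjects. It reaches 3.5 points (94.9% to 91.4%) only for a shift equal to the target effect in half the subjects.

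These figures rest on the section 12.2 planning values, on assumed values of f and s, and on uptake and draw order being unrelated to sequence. Randomization and blinding support that last condition, and nothing in the documents suggests that it fails.

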## **7 POTENTIAL RISKS AND BENEFITS**

### **7.1 Potential Risks Associated with Rifaximin**

Short term use of rifaximin is well-tolerated and frequencies of adverse events associated with this drug are similar to placebo. To date, there have been no randomized clinical trials in HIV-positive subjects. In several studies examining the effects of the drug as maintenance therapy in subjects diagnosed with decompensated liver disease and hepatic encephalopathy, as well as subjects diagnosed with irritable bowel syndrome, the emergence of treatment-emergent adverse effects (TEAEs) were similar in subjects randomized to placebo and rifaximin [19] [103]. The following adverse events have been reported in greater than 2% of subjects taking the 200 mg dose of rifaximin: flatulence, headache, abdominal pain (not otherwise specified), rectal tenesmus, defecation urgency, nausea, constipation, pyrexia, vomiting (not otherwise specified). The package insert accompanying this protocol provides information of side effects observed in less than 2% of subjects. The following events have been observed in the post-marketing experience: hypersensitivity reactions including exfoliative dermatitis, rash, angioneurotic edema, urticaria, flushing, and pruritus[98]. The 550 mg dose of rifaximin has been approved for use in patients with hepatic encephalopathy. At this dose in patients with hepatic encephalopathy [HE] the following events have been described in >5% of the patients (these include adverse events that may be attributable to the disease) peripheral edema, nausea, dizziness, fatigue, ascites, muscle spasms, pruritus, abdominal pain, abdominal distension, anemia, cough, depression, insomnia, nasopharyngitis, abdominal pain upper, arthralgia, back pain, constipation, dyspnea, pyrexia, rash. The 550 mg dose of rifaximin will be used for this study. [103]

#### **Other Risks Associated With Rifaximin**

Similar to other antibiotics, rifaximin use has been associated with *C. difficile* infection. In studies where rifaximin has been studied as maintenance therapy the incidence of *C. difficile* infection in subjects receiving rifaximin were no greater than the placebo arm and were similar to the background rates in this population. Subjects will be followed closely for the development of diarrhea, fever, abdominal cramps, or bloody stools [19]. In general, use of antimicrobial therapy may be associated with the emergence of bacterial resistance. Studies have demonstrated emergence of resistance with rifaximin therapy [80]. The consequences of this event are unknown and subjects will be monitored closely for any bacterial infection during therapy. While all risks to the subjects cannot be anticipated, all reasonable attempts will be made to ensure subject safety. This will include the evaluations outlined in Table 1.

## 7.2 Risks Associated with Colonoscopy and Biopsy

Diagnostic colonoscopy is generally safe and well tolerated, even in high-risk patient groups [104]. Actually, the majority of morbidity and mortality from these diagnostic procedures is related to cardiopulmonary complications of conscious sedation (aspiration or gastric contents, arrhythmia, hypoxemia) [105] with rates of attributable adverse outcomes and fatality of 0.54% and 0.03% respectively. While perforation is an exceedingly unlikely event, a risk for perforation exists, and the consequences of perforation include peritonitis, systemic sepsis, and death [106]. Bleeding and infection are other risks associated with this procedure. As a general practice, this risk is minimized by monitoring pulse, blood pressure, and oxygen saturation throughout the procedure. For colonoscopy, the reported mortality rates are 2-6 deaths/10,000 colonoscopies [107]; patients at the NIH Clinical Center are informed that the complication rates with colonoscopy are 2-4 perforations/1,000 colonoscopies, 10 perforations/1,000 colonoscopic polypectomies, 25 clinically significant bleeding episodes/1,000 colonoscopic polypectomies, 1 death/10,000 colonoscopies, and 2 deaths/10,000 colonoscopic polypectomies. Colonic perforation during lower endoscopy is almost exclusively associated with excess tension due to scope movement, inadvertent passage of an instrument (biopsy forceps, e.g.) through the wall, or over-insufflation of a segment of bowel and is reported to range from 0.03 to 0.65% for diagnostic colonoscopy and 0.073 to 2.14% in therapeutic procedure[108]. On the other hand, it is generally accepted that endoscopic biopsy-related perforation of the colon is a rare event overall, though it has been recognized to occur anecdotally in particular settings: in an area of atrophic mucosa over thinned bowel musculature [109] and in the ceca of elderly patients with bowel walls thinned by distension with air and (likely ischemia-related) mucosal ulceration and inflammation [110]. Similarly, clinically significant bleeding after colonoscopic mucosal biopsy is “exceedingly rare” [111] with no episodes of significant bleeding (requiring post-procedural evaluation or treatment) after cold biopsy in 2 series [112-113] and an estimate of minor bleeding (asymptomatic, self-limited, spotting on toilet paper or coloring toilet water) of 2.2% [112]. We could find no data relating specifically to the risk of bleeding to the number of biopsies taken per procedure. Only one published report of a single episode of major bleeding following a single cold biopsy of the cecum could be found [111]. Because of the large number of biopsies planned per endoscopy, we will inform the subjects of the potential for an increased risk of bleeding and perforation. In order to prevent complications and minimize their impact, we will avoid biopsies within ulcerated regions (where relative thinning of the gut wall may be present), avoid over-insufflation during biopsies, and provide post-procedure instructions for patients to recognize early warning signs of significant complications (abdominal pain, fever, persistent hematochezia) while providing mechanisms for early evaluation and treatment. In addition, experienced gastroenterologists will perform the colonoscopies to minimize the risk of complications related to this procedure.
